4.5 Safety Analysis

Adverse events (AEs) and serious adverse events (SAEs)

AEs will be coded by using the Medical dictionary for regulatory activities (MedDRA) version 23.0.

A treatment emergent adverse event (TEAE) is defined as an AE with AE onset date \geq date of first study medication. If a date is unknown or incomplete and the AE cannot definitely be considered as started before date of first study medication, the AE will be considered as TEAE, unless the AE resolution date is before the date of first study medication.

An AE overview table will be prepared showing the number of patients with at least 1 AE and at least 1 TEAE, TEAEs related to IMP, TEAEs related to IMP procedure (infusion), serious TEAEs, serious TEAEs related to IMP and serious TEAEs related to IMP procedure (infusion) as well as the total number of events in each category.

TEAEs as well as serious TEAEs will be tabulated by system organ class and preferred term (MedDRA). The number of events, as well as the number and rate of affected patients will be reported for each treatment group. Additional tables will be provided for TEAEs (system organ class and preferred term) summarized by severity, by relationship to IMP and by relationship to IMP procedure (infusion).

AEs that occur with AE onset date < date of first study medication are defined as “pre-treatment” events. All AEs for patients without treatment will be considered as pre-treatment AEs. Pre-treatment AEs will be listed only.

Individual patient data listings will be provided for all SAEs as well as additionally for all deaths only (AEs with outcome ‘Fatal’), unexpected adverse drug reactions as confirmed by the sponsor’s drug safety manager (AEs of patients with primary reason for discontinuation ‘Occurrence of a severe adverse reaction (SAR)’), discontinuation of IMP due to AEs (AEs with action taken regarding IMP ‘Drug interrupted’ or ‘Drug withdrawn’), or premature trial termination due to AEs (AEs of patients with primary reason for discontinuation ‘Adverse events necessitating withdrawal from the clinical trial’).

The important risks such as multi-organ failure, hypersensitivity, adverse hemodynamic effects and cardiovascular effects will be documented as AEs and will be listed and tabulated by system organ class and preferred term (MedDRA) for treatment emergent adverse events. The number of events, as well as the number and rate of affected patients will be reported for each treatment group. Pre-treatment emergent adverse events will be listed only.

Vital signs

Vital signs include Systolic blood pressure, Diastolic blood pressure, Heart rate, Body temperature and Respiratory rate.

Basic statistics will be computed for absolute values and the absolute change from baseline.

Vital signs will be tested before and after each dose (within 30 min before/after IMP administration) and only once at the visits without IMP. Baseline is defined as Screening value. Daily mean values of assessments before/after IMP administration will be used for calculation of absolute change from baseline at visits with IMP administration.

Oxygen saturation (part of vital signs, but measured only once per visit)

Oxygen saturation will be presented using basic statistics of absolute values for all visits and change from baseline for all after baseline visits.

Clinical laboratory assessments

All continuous results of laboratory data will be converted to standard unit before any calculation if needed. Conversion of all lab values will be described in a separate document.

Value evaluation (Normal / Abnormal – CS / Abnormal – Not CS) will be summarized for all laboratory parameters using frequency table additionally.

Absolute values as well as absolute change from baseline for the following laboratory data will be analysed by visit using basic statistics:

- Biochemistry: AST (GOT), ALT (GPT), Alkaline Phosphatase (AP), Total bilirubin, Total protein, Uric acid, Potassium, Sodium, Albumin, Urea Nitrogen (BUN), Creatinine, eGFR

(assessment is calculated according to the formula used in local laboratory: CKD-EPI, Cockcroft-Gault or MDRD)

- Inflammatory indicators: C-reactive protein (CRP), ESR, Procalcitonin
- Myocardial enzymes: Creatine kinase (total), CKMB, LDH, [alpha] - hydroxybutyrate dehydrogenase ([alpha] -HBD), Troponin (cTnl), Blood lactic acid
- Hematology: Red blood cells (RBC), Hematocrit, White blood cells (WBC), Hemoglobin, Platelets
- Coagulation: Prothrombin time (PT), Activated partial thromboplastin time (APTT), D-dimer, FIB
- Urinalysis: pH, Microscopic examination Red blood cells (BLD), Microscopic examination White blood cells (LEU)
- Stool routine and occult blood: Red blood cells (RBC), White blood cells (LEU)

Frequencies will be provided for the following categorical laboratory results by visit:

- Urinalysis: Glucose, Protein, Red blood cells (BLD), White blood cells (LEU)
- Stool routine and occult blood: Red blood cells (RBC), White blood cells (LEU), Occult blood

All abnormal evaluations (CS as well as not CS) for all laboratory assessments collected in eCRF will be listed.

ECG parameters

ECG evaluation (Normal / Abnormal – CS / Abnormal – Not CS) will be summarized using frequency table.

All clinically significant abnormal ECG values inclusive all ECG parameters (Heart rate [bpm], RR interval [ms], PR interval [ms], QT interval [ms], QRS complex [ms]) will be listed as well.

Detection of viral nucleic acid or viral gene sequencing

Detection of viral nucleic acid or viral gene sequencing data will be presented using frequency tables and listing.

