8.3.3.1 Withdrawal of Patients from the Clinical Trial

The following circumstances may lead to discontinuation of the study by an individual patient who will then be recorded as a drop-out, include but are not limited to the following:

- Withdrawal for personal reasons
- AEs necessitating withdrawal from the clinical trial
- Occurrence of a severe adverse reaction (SAR)
- Sudden incidence of diseases
- Circumstances in which the health of the patient would be endangered upon continued participation in the clinical trial
- Lost to follow-up
- Other (must be specified)

If a patient withdraws from the study at any time either at his or her request or at the investigator's discretion, an "End-of-Study/Early Termination" visit should be performed and the "End of Study" eCRF section should be used to collect the relevant information. The visit may also be performed as a phone visit or in-home visit (in Russia). The reason(s) for withdrawal must be recorded on the relevant page of the patient's eCRF and the patient's source data. Patients discharged from hospital before day 28 will be contacted by telephone to assess if they are alive at day 28.

It is vital to obtain follow-up data for any patient withdrawn from the study because of an AE. Every effort must be made to undertake protocol-specific safety follow-up procedures. If a patient is discontinued due to an AE, the event should be followed up until resolution or until the event becomes chronic.

The Data Safety Monitoring Board may also recommend withdrawal of patients.

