8.3.3.2 Premature Treatment Discontinuation

Patients must stop the IMP if the patient experiences any kind of hypersensitivity reaction. The patient may remain in the study and continue to attend study visits.

Patients may be withdrawn from the IMP after initiation of infusion if in the opinion of the investigator or of the Medical Monitor there is a risk to the patient's safety if they further receive IMP. If the patients are withdrawn from IMP, they may remain in the study and continue to attend study visits.

IMP treatment can be stopped early if a patient will be discharged before day 7.

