All AEs must be followed to closure (i.e. the patient's health has returned to his/her baseline status or all variables have returned to normal), an outcome is reached, stabilization (the investigator does not expect any further improvement or worsening of the event), or the event is otherwise explained regardless of whether the patient is still participating in the clinical trial and clinical judgment indicates that further follow-up is not warranted. When appropriate, medical tests and examinations are performed so that resolution of event(s) can be documented.

Moreover, elective procedures (planned at time of randomization, e.g. catheter intervention of a coronary stenosis) will be determined as expected AE.

8.5.2.2.13.1.1 Severity Categorization

The severity of AEs must be recorded. If the severity of an AE/SAE changes, or if there are any other changes they must be made within the same AE record. Also, only the highest severity needs to be recorded. Worsening of pre-treatment events from the medical history, after initiation of IMP treatment, must be recorded as new AEs.

The medical assessment of severity is determined by using the following definitions:

Mild: Symptom barely noticeable to patient; does not influence performance or functioning. Prescription drug not ordinarily needed for relief of symptom but may be given because of personality of patient.

Moderate: Symptom of a sufficient severity to make patient uncomfortable; performance of daily activities influenced: patient is able to continue in clinical trial; treatment for symptoms may be needed.

Severe: Symptom causes severe discomfort. May be of such severity that patient cannot continue in clinical trial: Severity may cause cessation of treatment with test drug; treatment for symptom may be given and/or patient hospitalized.

The term "severe" is here used to describe the severity/intensity of the specific event; it is not the same as "serious", which is based on patient/event outcome or action criteria.

8.5.2.2.13.1.2 Relationship Categorization

An investigator assesses each AE for its relationship to the IMP.

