8.7.1.2.4 Statistical Analysis

Continuous variables will be summarized with means, standard deviations, medians, lower and upper quartiles, minimums and maximums. Frequencies and percentages will be used to summarize categorical variables.

For time-to-event analyses censoring information will be used.

It is assumed that no patients will discontinue the study early prior to day 28 or hospital discharge in this Covid-19 setting. It is also assumed, that only very few missing values will arise due to not done evaluations. No imputation of missing values (e.g., no last observation carried forward (LOCF)) is planned, unless stated otherwise.

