8.7.1.2.7 Safety Endpoint

The safety evaluations will include analyses of AEs and SAEs, changes in vital signs, clinical laboratory assessments and in ECG parameters. The analysis of safety will be based on the SAF.

AEs

Pre-treatment AEs will be analyzed separately based on all patients included into the trial. AEs will be summarized by system organ class and preferred term according to Medical Dictionary for Regulatory Activities (MedDRA). The number of events, as well as the number and rate of affected subjects will be reported. AEs (system organ class and preferred term) will also be summarized by seriousness, by severity and by relationship to study medication. No statistical testing procedures will be applied to the analysis of AEs.

Individual patient data listings will be provided for all deaths, patients with other SAEs, unexpected adverse drug reactions (as confirmed by the sponsor's drug safety manager), discontinuation of IMP due to AEs, or premature trial termination due to AEs.

Vital signs

For vital signs, body temperature and body weight standard descriptive summary statistics will be calculated at each scheduled time point

Furthermore, standard descriptive summary statistics will be computed for the absolute change from baseline to each scheduled visit up to the last individual time point

Laboratory measurements

Laboratory data will be subjected to both a quantitative analysis (descriptive summary statistics) and qualitative analysis where frequencies of normal, above normal and below normal values will be computed.

The following analyses will be performed:

- Standard descriptive summary statistics will be calculated at each scheduled measuring time point
- Standard descriptive summary statistics will be calculated for the absolute change from baseline to each scheduled visit
- Frequencies of normal, above normal, and below normal values will be computed at each scheduled measuring time point
- Shift tables displaying changes with respect to the normal range between baseline and each scheduled visit will be provided
- A listing of all patients with abnormal (above normal or below normal) values at any time point will be given

Findings from ECG (12-lead)

Frequencies for the respective categories of (ab)normality will be tabulated.

A patient data listing of all clinically significant abnormal ECG values will be provided.

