 4.7 Missing Values22

 4.8 Data Base Closure and Blind Data Review Meeting (BDRM)22

 4.9 Miscellaneous23

5 CHANGES FROM PROTOCOL25

6 SIGNATURES26

List of Abbreviations

In the following abbreviations are listed as used within this statistical analysis plan or which might occur within the tables, listings and graphs outputs:

AE	Adverse event
ATC	Anatomical therapeutic chemical
BDRM	Blind data review meeting
BID	bis in die, i.e. twice daily
BMI	Body mass index
CM	Concomitant medication
CRF	Case report form
CS	Clinically significant
DSMB	Data safety monitoring board
ECG	Electrocardiogram
eCRF	Electronic case report form
FAS	Full analysis set
IMP	Investigational medicinal product
LDH	Lactate dehydrogenase
MedDRA	Medical dictionary for regulatory activities
MH	Medical history
N	Number of patients
NCS	Not clinically significant
PE	Physical examination
PP	Per protocol set
PT	Preferred term
SAE	Serious adverse event
SAF	Safety analysis set
SAP	Statistical analysis plan
SAR	Serious adverse reaction
SD	Standard deviation
SOC	System organ class
SOFA	Sequential organ failure assessment
mSOFA	Modified sequential organ failure assessment
SUSAR	Suspected unexpected serious adverse reaction
TLG	Tables, listings, graphs
VFD	Ventilator-free days
WHO	World health organization
WHO-DD	World health organization drug dictionary

1 General

This Statistical Analysis Plan (SAP) was defined by the Sponsor and the responsible Statistician without knowledge of the randomization code. It is based upon the Study Protocol (version 7.0 of 10Aug2020) and contains detailed description of the statistical methods described therein.

The SAP describes prospectively the analyses to be performed on study data for final analysis. It was finalized prior to data base lock and unblinding.

This SAP serves as SAP for final analysis and includes relevant endpoints for final analysis only. Details of outputs are given in Appendix A.

The DSMB analyses are described in a separate 'SAP for DSMB'.

Methodology

This is a Phase II prospective, multi-centre, double-blind, randomized, placebo-controlled, interventional trial to assess clinical safety, tolerability, and efficacy of APN01 on top of best standard of care in patients with severe COVID-19 and to evaluate if treatment with APN01 on top of standard of care is superior to placebo (NaCl 0.9%) on top of standard of care.

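### The SAP fills the listing of unexpected adverse drug reactions by reason for leaving the study, a condition that the protocol does not set and the SAP does not declare

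*SAP*

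**What the plan says.** Protocol 8.7.1.2.7 (Safety Endpoint) promises individual listings of several kinds of event. One is for "unexpected adverse drug reactions (as confirmed by the" sponsor's drug safety manager. It attaches no condition on study status.

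SAP 4.5 (Safety Analysis) repeats that title and then states in brackets what goes into the listing: "drug safety manager (AEs of patients with primary reason for discontinuation", where the reason named is "Occurrence of a severe adverse reaction (SAR").

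That category is one of the reasons listed in Protocol 8.3.3.1 for "discontinuation of the study by an individual patient who will then be recorded as a drop-out". It is therefore a reason for leaving the study, not a classification of an event. For patients who must stop study drug after a hypersensitivity reaction, Protocol 8.3.3.2 says: "The patient may remain in the study and continue to attend study visits". The same section says the same of patients taken off study drug for another safety risk.

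SAP section 5 lists the changes from the protocol on statistical aspects. It names the wording of the WHO scale endpoint and the coding of age, and nothing about this listing.

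**The concern.** The title of the listing and its selection rule describe different things. The title is about events: reactions judged unexpected by a named function. The rule is about patients: those who left the study for one particular primary reason. A programmer who follows the SAP exactly will produce a listing whose contents do not match its heading.

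The risk is one of interpretation. A short or empty listing under this title could be read in the study report as showing that few or no unexpected reactions occurred, when the rule would not have found most of them. A reader could also take the unrelated events of a patient who left as confirmed unexpected reactions.

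**Working it through.** The plan gives no figure to reproduce and no arithmetic applies. The check applies each document's rule to every type of case.

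**Is the bracket a selection rule?** In the same SAP sentence, the listing of deaths is followed by a bracket giving the AE outcome to be selected, and the listing of study drug discontinuations by a bracket giving the action-taken codes. Both are data selections. The bracket after the unexpected reactions has the same form and is naturally read the same way.

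**Which events does each document's rule select?**

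| Case | Protocol 8.7.1.2.7 | SAP 4.5 bracket |
|---|---|---|
| Confirmed unexpected reaction, study drug continued, patient stays in study | listed | not listed |
| Confirmed unexpected reaction, study drug stopped, patient stays in study | listed | not listed here |
| Confirmed unexpected reaction, patient leaves with another primary reason (AE necessitating withdrawal, personal reasons, lost to follow-up) | listed | not listed here |
| Confirmed unexpected reaction, patient leaves with SAR as primary reason | listed | listed |
| Severe but expected reaction, patient leaves with SAR as primary reason | not listed | listed |
| Any other AE of that patient, including mild or unrelated ones | not listed | listed |

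The two rules agree in one row of six.

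**Does the SAR category stand in for unexpectedness?** No. In its AE severity definitions the protocol says that the term severe "is here used to describe the severity/intensity of the specific event" and separates it from serious. Neither term says whether a reaction was expected. The abbreviation is also unstable: the protocol's list and the text of SAP 4.5 expand SAR as severe, whereas the SAP's own list of abbreviations gives "Serious adverse reaction".

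**How many patients would the rule reach?** Protocol 8.7.1.2.4 states: "It is assumed that no patients will discontinue the study early prior to day 28 or hospital discharge in this Covid-19 setting". If that held, nobody would leave for a reaction before that point, and the listing would be essentially empty however many unexpected reactions had been confirmed.

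**What else would show these events?** SAP 4.5 also provides a listing of all SAEs, a listing of AEs with study drug interrupted or withdrawn, a listing and table of important risks (multi-organ failure, hypersensitivity, hemodynamic and cardiovascular effects), and tables of treatment-emergent AEs by relationship to study drug and to the infusion. Protocol 8.5.3.2.1 adds a per-patient AE listing. None of these is described as carrying an indicator of unexpectedness.

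**The case against.** The strongest reply is that little is lost, and much of it stands. Four stronger readings are tempting, and the documents do not support them.

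- A reader might infer that a hypersensitivity reaction in a patient who stays in the study would go unreported. It would be absent from this listing only. Study drug must be stopped, so a correctly coded event falls in the interrupted-or-withdrawn listing, and hypersensitivity is also listed and tabulated as an important risk.
- A reader might infer that non-serious unexpected reactions have no other listing. That is too broad. The events outside the other specific safety listings are those that are non-serious, did not change study drug, are not an important risk, and did not lead to withdrawal. Even these appear in the protocol's per-patient listing and, if treatment-emergent, in the relationship tables, though without a label.
- A reader might infer that the rule takes in the events of everyone who leaves, or ignores causality altogether. It reaches only those with SAR as primary reason, and calling something a reaction implies some judgment of relatedness for that patient. What is missing is a filter on each event.
- A reader might infer that regulators would miss these reactions. Serious unexpected reactions go to authorities through the expedited reporting in Protocol 8.5.2.2.13.2.6, which does not depend on this listing.

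The bracket could also be an extra condition on top of the drug safety manager's confirmation. The over-inclusion would then largely disappear, but the omissions would remain. SAP Appendix A, which gives output details, is not in the text available for this review. It might settle that reading, and its absence is not counted against the plan.

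**Conclusion.** The mismatch is real and minor. As SAP 4.5 is written, the listing omits confirmed unexpected reactions in patients who remain in the study or leave for any other primary reason. On the plain reading of the bracket, it also includes all AEs of patients who leave with SAR as primary reason. The omission holds on either reading of the bracket; the over-inclusion depends on the plain one. The departure from Protocol 8.7.1.2.7 is not declared in SAP section 5.

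The consequence is limited to one listing. No endpoint, test, sample size or safety table changes, and most of the events concerned are visible elsewhere. What is lost is the only described output meant to identify events as unexpected.

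**What to change.** Replace the bracket in SAP 4.5 with a selection on events: those AEs that the sponsor's drug safety manager has confirmed as unexpected and related to study drug, regardless of whether the patient stopped treatment or left the study. This is what Protocol 8.7.1.2.7 already describes.

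First check that the confirmation exists for non-serious events. Protocol 8.5.2.2.13 says AEs are classified for causality and seriousness and does not mention expectedness, so the documents do not show that it is recorded for all AEs. If it is not, either restrict the listing to the events for which it is assessed, or rename it to match what it selects, and declare the change in SAP section 5. Align the expansion of SAR at the same time.

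The cost is one revised SAP line and a small transfer of the drug safety manager's confirmation into the analysis dataset. If expectedness had to be newly assessed for non-serious events, the work would be larger, which is why restricting or renaming is offered as the alternative.

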8.5.2 Appropriateness of Measurements

8.5.2.1 Screening Procedures

Written, signed, and dated informed consent from the patients prior to the performance of any clinical trial related procedures must be obtained by an investigator. A copy of the signed consent form and the information sheet must be given to the patient for their records after signature and before enrollment.

The time period between start of screening procedures and start of treatment must not exceed 24 hours. In case the required screening procedures take less time, randomization and start of treatment could be performed also on the same day then screening. Pre-dose events other than biomarker sampling and vital signs do not need to be performed if randomization and screening are on the same day. The following events will be performed: check of inclusion and exclusion criteria, obtaining medical history and demographics, score assessment of WHO's 11-point scale, PCR analysis, vital signs, physical examination, serum or urine pregnancy test, lab assessments, ECG, assessment of respiratory condition, mSOFA-score.

See Table 1 for a complete list of screening procedures to be performed.

Only an authorized and trained investigator may decide on the eligibility of the patient.

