3.4 Assignment of Analysis Sets to Analysis

The FAS serves as the primary efficacy analysis set (as randomized). All efficacy analyses are based on the FAS. The SAF will be used for the evaluation of the safety assessments (as treated) unless stated otherwise. All biomarker analyses are based on SAF (as treated) as well. The PP will only be analyzed for main efficacy outcome measures (as treated).

4 Statistical Evaluation

Continuous variables will be summarized with means, standard deviations, medians, lower and upper quartiles, minimums and maximums. Frequencies and percentages will be used to summarize categorical variables.

The two different treatment groups (groups APN01 and Placebo) will be separately tabulated. Where appropriate total columns will additionally be displayed for the two treatment groups combined.

A detailed description of the planned tables, listings and graphs is given in Appendix A.

Baseline

Baseline is defined as last observation before treatment, i.e. Day 1 value or Screening value if Day 1 value is missing or if Screening and Day 1 is the same day, unless stated otherwise.

Visit terminology

Visit No.	Notation used on the case report form	Notation used for tables, listings and graphs
10	Screening (Day -1)	Screening
150	Unscheduled visit	Screening *
20	Day 1	Day 1
30	Day 2	Day 2
40	Day 3	Day 3
50	Day 4	Day 4
60	Day 5	Day 5
70	Day 6	Day 6
80	Day 7	Day 7
150	Unscheduled visit	Day 8 *
90	FU Day 10	FU Day 10
100	FU Day 14	FU Day 14
110	FU Day 28/EOS	FU Day 28/EOS
130	FU Day 28/EOS Phone Visit	FU Day 28/EOS
170	Russia only: Home Visit FU Day 28/EOS	FU Day 28/EOS
120	Early termination	ET
140	Early termination FU Day 28/EOS	ET
150	Unscheduled visit	Unscheduled visit

ET = Early termination

** IMP administration at Screening and at Day 8 as well as all related assessments (e.g. ECG, Vital signs, etc.) are documented in eCRF as IMP administration or assessment on Unscheduled visit and will be shown in TLGs as IMP administration or assessment on Screening and Day 8 respectively.*

Unscheduled visits will not be included in any tables or graphs, only in listings and will be displayed after all scheduled visits.

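### Vital-sign change from baseline on dosing days averages pre- and post-dose readings against Screening, which understates an effect seen mainly after the infusion

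*SAP*

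**What the plan says.** The SAP's vital-signs paragraph (section 4.5) sets the measurement schedule: "Vital signs will be tested before and after each dose (within 30 min before/after IMP administration) and only once at the visits without IMP". With twice-daily dosing that is normally four readings a day. The planned output is stated in one line: "Basic statistics will be computed for absolute values and the absolute change from baseline".

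Two rules then govern the change from baseline. The reference value: "Baseline is defined as Screening value". The on-treatment value: "Daily mean values of assessments before/after IMP administration will be used for calculation of absolute change from baseline at visits with IMP administration".

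The SAP's general definition (section 4, Baseline) is different: "Baseline is defined as last observation before treatment, i.e. Day 1 value or Screening value if Day 1 value is missing". It allows exceptions where stated, and it also falls back to Screening when Screening and Day 1 coincide. Protocol 8.5.2.1 keeps pre-dose vital signs compulsory even then: "Pre-dose events other than biomarker sampling and vital signs do not need to be performed if randomization and screening are on the same day".

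The same SAP section treats blood-pressure harm as a risk of interest: "The important risks such as multi-organ failure, hypersensitivity, adverse hemodynamic effects and cardiovascular effects will be documented as AEs". Those events are to be listed and tabulated.

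Protocol 8.7.1.2.7 plans vital-sign summaries by scheduled time point and changes from baseline by scheduled visit. It does not mention averaging readings within a day. SAP section 5, which lists departures from the protocol, does not mention it either.

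**The concern.** A pair of readings around each infusion lets each patient serve as his or her own control for an acute effect. Averaging the pair discards that contrast in the change-from-baseline table.

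Blood pressure deserves attention for this product. Protocol 6.2 describes its action as cleaving Angiotensin II. Protocol 6.5 reports a blood-pressure decrease of 7.92 mmHg in hypertensive rats. Protocol 6.6.6 reports no adverse systemic hemodynamic effects in pulmonary arterial hypertension, but notes that this experience is limited to single doses. Here up to 14 doses are given, each over 3 to 30 minutes. A reader who looks to the vital-sign change table for reassurance would see a smaller shift than the post-dose readings showed.

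**Working it through.** The documents give no figure for this point, so there is none to reproduce. The check is arithmetic on the stated rule.

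**Inputs.** Readings before and after each dose, Screening reference and daily mean: SAP 4.5. Dosing every 12 hours: Protocol 8.1. Half-life 9.6 hours: Protocol 8.4.5. Let *d* be the size of the post-dose fall and *f* the fraction of it still present at the next pre-dose reading. The documents do not give *f*, so a range is shown.

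**Step 1: share retained by the daily mean.** On a day after treatment has begun, the four readings are shifted by *fd*, *d*, *fd*, *d*. Their mean is *d*(1 + *f*)/2, so the share retained is (1 + *f*)/2. On a Day 1 with two doses, the first pre-dose reading is untreated. The shifts are then 0, *d*, *fd*, *d*, and the share is (2 + *f*)/4.

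**Step 2: a value for *f*.** Assume that the effect decays with the half-life. Then *f* = 2^(-12/9.6) = 0.42. Later days retain (1 + 0.42)/2 = 71%; a two-dose Day 1 retains (2 + 0.42)/4 = 61%.

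**Step 3: a 10 mmHg post-dose fall on later days, with no drift.**

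| *f* | Daily mean (SAP rule) | Post minus pre, *d*(1 - *f*) | Post-dose minus value before first dose |
|---|---|---|---|
| 0 | 5.0 (50%) | 10.0 (100%) | 10.0 |
| 0.25 | 6.25 (62.5%) | 7.5 (75%) | 10.0 |
| 0.42 (assumed decay) | 7.1 (71%) | 5.8 (58%) | 10.0 |
| 0.5 | 7.5 (75%) | 5.0 (50%) | 10.0 |
| 1 | 10.0 (100%) | 0 (0%) | 10.0 |

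For illustration only, a fall of the size seen in rats, 7.92 mmHg, would appear as 3.96 mmHg at *f* = 0.

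**Step 4: where post-minus-pre falls short.** The daily mean retains more than post-minus-pre when (1 + *f*)/2 > 1 - *f*, that is, when *f* > 1/3. Post-minus-pre isolates an acute effect best but understates one that carries over. It therefore has to be paired with change from a baseline taken before the first dose.

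**Step 5: drift since Screening.** With *f* = 0, the tabulated within-arm change is drift - *d*/2. A 10 mmHg fall with an assumed 5 mmHg rise since Screening gives 5 - 5 = 0. If the placebo arm drifts by the same 5 mmHg, it shows +5, and the contrast between arms is 0 - 5 = -5 mmHg. The contrast is halved but not removed.

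**Step 6: the reference value.** If the protocol is followed, every treated patient has a vital-sign reading just before the first dose. The Screening label also has a loose edge. SAP sections 4 and 4.3 relabel assessments linked to a dose given at the Screening visit as Screening, so for those patients the label alone does not exclude a post-dose reading.

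**The case against.** The strongest reply is that the rule governs only one table. SAP 4.5 also summarises absolute values. It tabulates hemodynamic events as adverse events, and treatment-emergent events by relationship to the infusion procedure. Protocol 8.5.3.2 adds a review of individual values. A 12-lead ECG with heart rate is done within 30 minutes after dosing (Protocol 8.5.2.2.8), so the paired readings are not the only check on an acute effect. This stands. A reader might infer that the report cannot show a hemodynamic effect at its true size; the documents do not support that. Appendix A, which holds the table layouts, is not available and may split the readings.

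The wording of the averaging rule could also mean one daily mean of pre-dose readings and another of post-dose readings. Pooling is the more natural reading, but if two means were intended, the SAP should say so.

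The Screening reference is a permitted exception to the general definition. Screening must start no more than 24 hours before treatment, and drift should be similar in randomised arms. This also stands: the reference value plays no part in the dilution and can mask only a within-arm change.

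Two other stronger readings fail. One is that any effect is halved; exact halving needs no carry-over at all. The other is to express the loss as statistical power. No test of vital signs is planned, and the documents give no standard deviations from which to compute it.

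**Conclusion.** The point holds as a dilution in one descriptive safety table. On the pooled reading of the rule, the change from baseline retains 50% of a purely post-dose effect, about 61-71% under the half-life assumption, and all of it only if the effect persists unchanged to the next dose. That range assumes a same-sized effect after each dose. Drift since Screening may add to or offset the within-arm figure, while the between-arm contrast is attenuated but not erased.

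The loss is avoidable, because the paired readings exist, yet the SAP text plans no summary that uses the pairing. The averaging is also an addition to the protocol's plan that section 5 does not declare. The primary analysis is untouched. This is an inexpensive improvement to safety reporting and not a threat to the trial's conclusions.

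**What to change.** In SAP 4.5, replace the daily-mean rule with separate summaries by arm of:

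- (i) pre-dose values, as change from the last value before the first dose;
- (ii) post-dose values, as change from that same value;
- (iii) post-minus-pre change for each infusion.

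The lowest post-dose blood pressure per day is an optional addition. Items (i) and (ii) are needed alongside (iii), because post-minus-pre alone understates an effect that carries over.

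For the baseline, follow the principle of the SAP's general definition, "Baseline is defined as last observation before treatment". State explicitly that for vital signs this is the last reading before the first dose, including when Screening and Day 1 are the same day. That also removes the ambiguity over readings relabelled as Screening. If any within-day averaging is kept, list it in SAP section 5.

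The cost is SAP wording and a few more descriptive tables from readings already collected. No test, endpoint or sample size changes.
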